5.5 Duration of Therapy

In the absence of treatment delays due to adverse event(s) or disease progression, treatment may continue for 26 courses (approximately two years) or until one of the Off Treatment Criteria found

in Section 5.6 applies.

During the second year of treatment, procedures consistent with good clinical care will continue. Patients will be seen monthly for medical history, physical exam (including height, weight, vital signs, and performance status), neurologic exam, dates of drug administration, relevant laboratory evaluations and routine neuro-imaging assessments. Therapy-related events will be recorded per standard assessments, including adverse events, date of disease progression, date of last follow up, date patient goes off treatment and date off study. Please review the table in Section 10 of the protocol for the required assessments and intervals. All patients must discontinue treatment with selumetinib following the completion of 26 courses of treatment.

5.6 **Duration of Follow Up**

Discontinuation of Treatment

At the discontinuation of treatment, the "Off Treatment Date" is to be recorded in the CRF and is to be consistent with the reason given for going off treatment. The "Last Treatment Date" is defined as the last date that the patient received protocol based therapy. Date of "off treatment" must be the greatest of the date of last treatment, date of procedure, date of patient assessment, notification of patient/family decision, or decision made by the physician that resulted in the patient being taken off protocol treatment. The reason for discontinuation of treatment must be documented by the attending investigator in the medical record and recorded in the CRF. The "Off Treatment Date" and the "Last Treatment Date" should be the same for patients that complete all protocol defined treatment.

Patients will be considered Off Treatment for the following reasons:

- 5.6.1 Development of unacceptable toxicity as outlined in Section 5.2.1 that does not resolve within 14 days.
- 5.6.2 Non-compliance with study guidelines
- 5.6.3 Progressive disease, as outlined in section 11.1 and 11.2
- 5.6.4 Development of a medical or psychiatric illness, that in the investigator's judgment renders the patient incapable of further therapy on this protocol
- 5.6.5 The patient, parent or legal guardian refuses further treatment on this protocol
- 5.6.6 Pregnancy
- 5.6.7 Completion of maximum number of courses of treatment with selumetinib

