
Patients will be monitored every 6 months for 2 years after protocol treatment. Ongoing AE's should be monitored as per section 7.4.3. Additionally, patients will be followed for initiation of subsequent therapy for NF2, selumetinib related adverse events (including cardiac toxicities), date of disease progression, date of last follow up, and date of death.

Patients who are off protocol therapy must be followed until an Off Study Criterion is met. Ongoing AE's should be monitored as per section 7.4.3.

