5.7 Criteria for Removal from Study

The date and reason for the patient coming off study must be documented in the CRF.

- 5.7.1 Patient determined to be ineligible (Treatment with selumetinib was never started).
- 5.7.2 Patient determined to be ineligible (Treatment with selumetinib WAS started).

These patients must be observed for 30 days following date deemed ineligible. All AE's must be recorded in that 30-day period.

- 5.7.3 Patient, parent, or guardian withdraws consent for continued participation.
- 5.7.4 Patient death while on study. The IRB, Sponsor, and FDA must be notified as per Section 7
- 5.7.5 Patients removed from treatment for progressive disease (PD) be observed for 30 days following last dose of selumetinib.
- 5.7.6 Commencement of additional anti-cancer therapy
- 5.7.7 Completion of protocol defined follow up

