10 STUDY CALENDAR

	Pre- therapy	Courses 1-12 ^H	Courses 13-26 ^H	Completion/ Discontinuation Of Treatment
PHYSICAL ASSESSMENTS				Ì
Medical history	X	X ^A	X	X
Physical exam /height/weight	X	X ^A	X	X
Vital signs	X	X ^A	X	X
Performance status	X	X^{A}	X	X
Neurologic exam	X	X ^A	X	X
Smoking Status	X			
Hearing evaluation (stratum 1)#	X	X ^C	X^{C}	
LABORATORY EVALUATIONS				
CBC - WBC, HgB, Hct, Platelets, ANC, ALC B	X	X ^A	X^{A}	X
PT and INR for those patients on warfain		X	X	
Serum Chemistry - Sodium, Potassium, Bicarbonate, Chloride, Calcium, BUN, Creatinine, Glucose, Phosphorous, Magnesium, Albumin, Total Protein ^B	X	X ^A	X^{A}	X
SGPT (ALT), SGOT(AST), Alkaline phosphatase, Total Bilirubin ^B	X	X ^A	X^{A}	X
CPK **	X	X ^A	X^{A}	
Serum or urine pregnancy test (for females of childbearing potential)	X	X ^A	X ^A	
Echocardiogram (ECHO)	X	X ^C	X^{C}	
12-lead EKG	X			
Ophthalmology evaluation	x D	x ^D	x ^D	X
Pulse Oximetry	X			
Chest X Ray	\mathbf{X}^{E}			
Growth plate assessment	X	X ^C	X ^C	
IMAGING ASSESSMENTS				
Brain MRI	X	X ^C	X ^C	X
Spine MRI	X	X ^{C, F}	$X^{C, F}$	X F
CORRELATIVE STUDIES				
NF1-QOL	X	Every 3 courses	Every 4 courses	
Pre-trial tumor materials (if available)	X			

	Pre- therapy	Courses 1-12 ^H	Courses 13-26 ^H	Completion/ Discontinuation Of Treatment
--	-----------------	------------------------------	-------------------------------	--

- A. To be done prior to each course. See Section 5.3. Height does not need to be recorded for patients >18 years of age after initial measurement. Childbearing potential are those female patients who have reached menarche.
 - # Audiology will include measurement of pure tone thresholds and determination of word recognition scores
- B. To be done more frequently throughout the duration of treatment if required to monitor toxicities.
- C. To be done prior to initiation of therapy, after courses 3, 6, 9, 12, 16, 20, 26 until progression or end of therapy. The assessment is a tibial x-ray (AP and lateral views) of the right knee. If abnormalities are detected on routine X-rays, MRI scan of both knees should be performed. Growth plate assessments should be done for patients under the age of 18 only, unless growth plate closure is documented.
- D. Baseline and following any visual disturbance during treatment. See section 5.2
- E. To be done if pulse oximetry is < 95% or if clinically indicated during treatment. See section 5.2

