13.1.2 Evaluability for Response

All patients who receive study drug will be considered evaluable for response.

Each participant should be assigned one of the following categories: 1) hearing response, 2) stable hearing, 3) progressive hearing loss, 4) progressive disease 5) tumor response 6) early death from NF2-related condition, 7) early death from toxicity, 8) early death because of other cause.

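### Does the lack of a not-assessed entry in section 13.1.2 leave open how a treated Stratum 1 patient without a 24-week hearing test is counted?

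*Combined protocol and SAP*

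**What the plan says.** Section 13.1.2 sets the denominator: "All patients who receive study drug will be considered evaluable for response". Every patient is then "assigned one of the following categories: 1) hearing response, 2) stable hearing, 3) progressive hearing loss, 4) progressive disease 5) tumor response", followed by three kinds of early death. No entry covers a patient who was not assessed, and no category carries a time point.

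Sections 1.1.1 and 13.2 place the Stratum 1 primary endpoint at 24 weeks. Section 11.1.1 defines hearing response by the critical-difference table in Appendix E, without a visit. Section 13.2 applies a Simon two-stage rule: stop if 0 of 9 respond, otherwise treat 8 more, and call the drug successful with 3 or more responses.

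In the section 10 calendar, the row "Hearing evaluation (stratum 1") points to note C: "To be done prior to initiation of therapy, after courses 3, 6, 9, 12, 16, 20, 26 until progression or end of therapy". That row has no mark in the completion/discontinuation column, whereas brain MRI has one. Reasons to stop under section 5.6 include "Progressive disease, as outlined in section 11.1 and 11.2" and "The patient, parent or legal guardian refuses further treatment on this protocol". After treatment, "patients will be followed for initiation of subsequent therapy for NF2, selumetinib related adverse events (including cardiac toxicities), date of disease progression", together with last follow-up and death. Hearing tests are not listed. Section 5.7.5 adds: "Patients removed from treatment for progressive disease (PD) be observed for 30 days following last dose of selumetinib".

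**The concern.** Courses last 28 days, so the tests after courses 3 and 6 fall at weeks 12 and 24. A Stratum 1 patient who stops before the end of course 6 has no scheduled route to the primary measurement. Three situations look awkward:

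- **(a)** The patient stops before week 12, alive and without progression. Unless the discontinuation MRI shows a tumor response, no category fits.
- **(b)** The patient has a hearing response at week 12 and then stops. The first category fits, because section 11.1.1 names no visit, yet there is no 24-week response.
- **(c)** Hearing response and tumor progression occur together at week 12. Categories 1 and 4 both fit, and testing ends.

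If the category list decided the primary count, (b) could add a response that the 24-week endpoint does not contain, and (c) might. That could open stage 2 or change the final conclusion. In a single-arm trial, an unwritten rule might also be settled after the results are known.

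**Working it through.** **1. The plan's own figures (section 13.2).** Inputs: 9 then 8 patients; stop at 0 of 9; success at 3 or more of 17; rates 0.05 and 0.25.

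P(stop) = (1 − p)^9. With X ~ Bin(9, p) and Y ~ Bin(8, p):

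P(success) = P(X=1)·P(Y≥2) + P(X=2)·P(Y≥1) + P(X≥3)

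- p = 0.05: P(stop) = 0.630; P(success) = 0.2985×0.0572 + 0.0629×0.3366 + 0.0084 = 0.0466.
- p = 0.25: P(stop) = 0.075; P(success) = 0.2253×0.6329 + 0.3003×0.8999 + 0.3993 = 0.812.

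These agree with the stated 0.63, 0.05, 0.075 and 0.81.

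**2. How much one patient can matter.** Suppose one stage-1 patient is a week-12 responder without a 24-week test.

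| Rate in the other 16 | P(success), patient not counted | P(success), patient counted |
|---|---|---|
| 0.05 | 0.039 | 0.189 |
| 0.25 | 0.771 | 0.937 |

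The coding of such a patient does matter, so the question is whether the plan leaves it open.

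**3. What the text yields.** The denominator is every treated patient (13.1.2). The numerator is hearing response at 24 weeks (1.1.1 and 13.2). The decision rule follows that definition in the same paragraph of 13.2 and does not cite the list in 13.1.2. Section 11.1.1 has no visit attached because the same definition also serves duration of response. A treated patient without a 24-week score is therefore in the denominator and not in the numerator. This settles (a), (b) and (c) alike.

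**4. Error rates under that reading.** The documents give no rate of missing 24-week tests. Assume a share d of 10%, 20% or 30%.

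- If 5% and 25% are 24-week rates among all treated patients, Type I error stays 0.047 and power 0.81.
- If they are rates at the last available test, and untested patients respond at the same rate, the counted rate is p(1 − d). Type I error falls to 0.036, 0.026 or 0.019, and power falls to 0.745, 0.663 or 0.566.

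**5. Error rates if the last available test counted instead.**

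- If 5% is the all-treated 24-week rate, the counted rate is 0.05/(1 − d) = 0.0556, 0.0625 or 0.0714, and Type I error is 0.060, 0.080 or 0.109. This assumes every untested patient has a week-12 score and responds at the same rate as those tested.
- If the null rate at the last test is itself 5%, Type I error stays 0.047.
- If the null rate is 5% at week 24 but 0.15 at week 12, carrying week 12 forward gives 0.073 at d = 10% and 0.104 at d = 20%. The 0.080 above for d = 20% is therefore not a general upper bound.

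**6. How often the relevant patient would occur.** P(at least one untested patient among 17) = 1 − (1 − d)^17 = 0.83 at d = 10% and above 0.99 at d = 30%. An untested patient alone changes nothing, though. The relevant event is an untested patient with a week-12 response. If all untested patients have a week-12 score, its chance is 1 − (1 − d·p)^17:

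| Response rate p | d = 10% | d = 30% |
|---|---|---|
| 0.05 | 0.08 | 0.23 |
| 0.25 | 0.35 | 0.73 |

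A changed decision also needs the count to lie at a boundary.

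**The case for a change.** The best argument for a change is that the rule has to be inferred. No section says in words how a treated patient without a 24-week score is counted, and the label in 13.1.2 fits a week-12 responder. The first look has nine patients in an open single-arm trial, one patient can move the chance of success from 0.039 to 0.189 at the null rate, and the remedy would cost a few sentences. All of that is accurate.

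It does not show two equally open choices. Counting a week-12 result would mean letting a general list under an evaluability heading override an endpoint whose time point is stated twice. Case (c) is weaker still: with categories 1 and 4 both fitting, the list does not make that patient a response.

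The gap is also narrower than it first appears. Many patients without a 24-week test do have an entry: hearing loss at week 12 (category 3), tumor progression (4) or tumor response (5), and the discontinuation MRI can supply either of the last two.

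The one discontinuation figure in the documents gives little help with the likely rate. In section 2.2.2, 18 patients stopped for adverse events, which is 18/56 = 32% if the 56 in that paragraph is the denominator. It covers stopping at any time in an adult phase 1 study, and the listed dose cohorts sum to 6 + 7 + 7 + 8 = 28. It is not a rate of missing 24-week hearing tests.

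**Conclusion.** No change to the plan is needed. The missing not-assessed entry and the absent time point are real gaps in detail, but analysts who follow sections 1.1.1, 13.1.2 and 13.2 will count an untested Stratum 1 patient as a non-responder. A rule written out in full would say the same, so it would alter neither error rate.

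Under that reading, Type I error is 0.047 or lower. Any loss of power, to 0.57 at 30% untested if the planned rates describe the last available test, is the cost of missing tests under a conservative rule, and a clarifying sentence would not recover it. Inflation above 0.05 needs two things: a departure from the stated 24-week endpoint, and a null rate in the counted data above the planned 5%. All shares of untested patients used here are assumptions.

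The overlap of hearing and tumor categories, and the absence of a Stratum 2 stable-disease entry, affect how the category table reads but neither primary decision. A stable Stratum 2 patient is a non-responder for complete plus partial response either way.

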13.2 Study Design/Endpoints

The primary endpoint for the Stratum 1 is hearing response at 24 weeks, defined as an improvement in word recognition score above the 95% critical difference, taking as reference the baseline word recognition score (Appendix E). This primary objective of the efficacy of selumetinib will be addressed according to a Simon two-stage design. The first stage will consist of 9 subjects. If 0 of the 9 subjects have an efficacious response the study will terminate at the end of the first stage and the drug will be deemed ineffective. If 1 or more subjects have an

efficacious response, 8 additional subjects will be enrolled for the second stage. If both stages are completed and there are 3 or more efficacious responses then the drug will be considered successful, in the case of two or fewer desired responses the drug will be deemed ineffective.

The primary endpoint for the Stratum 2 is to estimate the sustained objective response rate (CR+PR). Stratum 2's primary objective of the efficacy of selumetinib will be also addressed according to a Simon two-stage design.⁴⁷ The first stage will consist of 9 subjects. If 0 of the 9 subjects have an efficacious response the study will terminate at the end of the first stage and the drug will be deemed ineffective. If 1 or more subjects have an efficacious response, 8 additional subjects will be enrolled for the second stage. If both stages are completed and there are 3 or more efficacious responses then the drug will be considered successful, in the case of two or fewer desired responses the drug will be deemed ineffective.

Using the described design, if the true probability of an efficacy is 0.05, then the probability of terminating at the end of the first stage (9 subjects) is 0.63. The total probability of concluding the drug is effective is 0.05. Under this low probability of efficacy the expected sample size is 12 subjects. If the true probability of an efficacy is 0.25, then the probability of terminating at the end of the first stage (9 subjects) is 0.075. Under this alternative probability of efficacy the power to conclude the drug is effective is 0.81. We anticipate that this trial will complete accrual in two years.

Simon Two-Stage Design

Simon⁴⁷ proposed a two-stage design primarily for use in phase 2 clinical trials where a single treatment arm is compared to a historical control. The stated objective of the design is to minimize the expected number of patients treated if the null hypothesis of no treatment effect is in true. Under this framework a design is conducted in two stages as follows. The total number of subjects that under consideration, N, is equal to the sum of the sample sizes from each stage, n_1 and n_2 , respectively. After the first n_1 subjects (the first stage) a criteria is set so that if fewer than this pre-specified criteria exhibit a response to treatment the trial is terminated and the treatment is deemed **ineffective**; otherwise, the final n₂ subjects are enrolled. After the second stage a different pre-specified criteria is used such that if fewer than this value exhibit a response the treatment is deemed ineffective; if a greater than or equal number of patients exhibit a response to treatment the null hypothesis is rejected and the treatment is declared effective. The expected sample size = n_1 * (the probability of termination after the first stage under the null hypothesis) $+ n_2$. The selection of the overall sample size, the sample sizes of each stage and the two pre-specified rejection/acceptance criteria are selected such that the expected sample size is minimized, a minimum power is obtained (usually around 0.8 or 0.90) and a desired level of significance (usual $\alpha \le 0.05$) is satisfied. This is considered to be an ethical solution to phase 2 trial design since it minimized the number of patients administered an ineffective treatment. Lee and Feng (2005) reviewed 126 phase II trials where the design was reported and found that 25% percent used a Simon two-stage design.

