1 OBJECTIVES

1.1 Primary Objectives

- 1.1.1 To assess the hearing response rate at 24 weeks using word recognition scores in children and young adults with NF2 who are treated with selumetinib on stratum 1
- 1.1.2 To determine the radiographic response rate of other NF2 related tumors (meningiomas and ependymomas) in patients treated with selumetinib on stratum 2.

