9.1.3 Special Studies - Neuroimaging Studies

Patients will have MRI brain and spine with and without contrast performed prior to initiation of therapy, after courses 3, 6, 9, 12, 16, 20, 26 until progression or end of therapy. MRI spine should be performed at the same time when obtaining MRI Brain when clinically indicated.

Stratum 1 patients: Volumetric measurements of VS: Traditionally, VSs have been measured using either 1-dimensional measurements (in the long axis) or 2-dimensional measurements (calculated by taking the square root of the product of the short axis-long axis measured to the plane perpendicular to the face of the temporal bone). However, the irregular shape of VSs, as determined by the unique anatomy of the IAC and cerebellopontine angle, makes it difficult for linear measurements to accurately and fully represent growth for the entire tumor. As a result, VS growth may be underestimated by linear measurement criteria. Semi-automated volumetric analysis overcomes these limitations since it uses data from 3 dimensions. The coefficient of variation (COV) ranges from 0.6% to 6.8% and is generally below 5% for lesions greater than 1 cc. 12 Volumetric analysis not only better reflects tumor size, but also allows accurate detection of smaller changes in tumor size compared to standard solid tumor response criteria (e.g., RECIST criteria). This ability to detect small changes in size is critical for tumors with slow growth rates such as VS, and, when used in clinical trials, helps limit exposure to potentially toxic and/or inactive agents. Trials for NF- related tumors, such as plexiform neurofibromas, are now routinely using volumetric changes as the primary endpoint, typically choosing a 20% increase for progression and 20% decrease for radiographic response. 45

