11.2.2.2 Partial Response

Partial Response (PR): Greater than or equal to 50% reduction in tumor size by bidimensional measurement, as compared with the baseline measurements, on a stable or decreasing dose of corticosteroids, accompanied by a stable or improving neurologic examination, and maintained for at least 8 weeks.

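### Does the missing assessment time for the Stratum 2 response undermine its 0-of-9 stopping rule?

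*Combined protocol and SAP*

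**What the plan says.** The Stratum 2 objective in section 1.1 is "To determine the radiographic response rate of other NF2 related tumors (meningiomas and ependymomas) in patients treated with selumetinib on stratum 2". Section 13.2 restates it: "The primary endpoint for the Stratum 2 is to estimate the sustained objective response rate (CR+PR)." Neither gives a time point, whereas Stratum 1 is fixed at 24 weeks in both places.

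Sections 11.2.2.1 and 11.2.2.2 supply the meaning of sustained. A partial response, for example, must be "accompanied by a stable or improving neurologic examination, and maintained for at least 8 weeks". Section 9.1.3 schedules MRI "after courses 3, 6, 9, 12, 16, 20, 26 until progression or end of therapy", and section 5.5 says that "treatment may continue for 26 courses (approximately two years)".

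The stage-1 rule in section 13.2 is "If 0 of the 9 subjects have an efficacious response the study will terminate at the end of the first stage". The sentence that follows it enrols eight more subjects if at least one of the nine responds, and success needs three or more of 17. The section closes its calculations with "We anticipate that this trial will complete accrual in two years".

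**The concern.** A two-stage rule needs to know when a patient counts as a non-responder. On scheduled scans, the earliest sustained response is first seen after course 3 (week 12) and confirmed after course 6 (week 24). The latest is first seen after course 20 (week 80) and confirmed after course 26 (week 104). Section 13.1.2 makes every treated patient evaluable without a minimum follow-up. Two failures then seem possible.

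- **Late read.** If the team waits for the full window and keeps enrolling, all 17 patients could be in before the stop can act. The expected size under the null would be 17 instead of the stated 12. If the team pauses instead, the two-year accrual forecast looks doubtful.
- **Early read.** If the rule is applied before slow responders have declared themselves, an active drug is stopped more often than the stated 0.075.

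The choice might also be made with results in view.

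Two smaller points sit alongside. The rule speaks of terminating the study, although there are two strata. The formula that begins "The expected sample size = n_1 * (the probability of termination after the first stage under the null hypothesis)" does not produce the stated 12.

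**Working it through.** **1. The plan's own figures.** Inputs from section 13.2: 9 subjects then 8; stop at 0 of 9; success at 3 or more of 17; response rates 0.05 and 0.25.

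P(stop at stage 1) = (1 − p)^9.

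- p = 0.05: 0.95^9 = 0.630
- p = 0.25: 0.75^9 = 0.075

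P(success) = 1 − P(X1 = 0) − P(X1 = 1)·P(X2 ≤ 1) − P(X1 = 2)·P(X2 = 0), with X1 ~ Bin(9, p) and X2 ~ Bin(8, p).

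- p = 0.05: 1 − 0.6302 − 0.2985 × 0.9428 − 0.0629 × 0.6634 = 0.047
- p = 0.25: 1 − 0.0751 − 0.2253 × 0.3671 − 0.3003 × 0.1001 = 0.812

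Expected size under the null = 9 + 8 × (1 − 0.630) = 11.96.

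All five stated values reproduce. They apply to each stratum, and they require each stage-1 patient's status to be final when the rule is read.

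**2. How late the read could be.** Assumptions: 17 Stratum 2 patients accrue evenly over 24 months, and nobody progresses or leaves early. Patient 9 enters at 9 ÷ (17/24) = month 12.7. Twenty-six courses last 26 × 28 ÷ 30.44 = 23.9 months. The last possible confirmation among the nine is at 12.7 + 23.9 = month 36.6.

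**3. What a late read costs.** Stage 2 enrolment is conditional on a response, so patients 10 to 17 may not be entered while the count is zero. An expected size of 17 would therefore describe a departure from the protocol. If the count stays at zero, enrolment ended at month 12.7 with nine patients, and the expected size remains 12. What is lost is calendar time.

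Accrual is prolonged only if a response does come, but late. The extreme case is a first response confirmed at month 36.6, after which eight more patients take 8 ÷ (17/24) = 11.3 months, ending at month 47.9. That is a corner case. When patient 9 enters, (12.7 − 5.5) × 17/24 ≈ 5 patients have already passed week 24. If a share f of eventual responders is confirmed by week 24 (assumed), the chance at p = 0.25 that at least one of the five has responded, so that no pause is needed, is 1 − (1 − 0.25f)^5:

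| f | chance of no pause |
|---|---|
| 1 | 0.76 |
| 0.75 | 0.65 |
| 0.5 | 0.49 |

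**4. What an early read costs, and whether a fixed scan does better.** Now let f be the share of eventual responders confirmed when zero of nine is read. The documents give no time-to-response data, so f is illustrative. The false stop is (1 − 0.25f)^9. If the final count is complete, power = Σ over k ≥ 1 of P(X1 = k)·[1 − (1 − f)^k]·P(X2 ≥ 3 − k). Under a fixed cut-off applied to both counts, the rate itself becomes 0.25f.

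| f | false stop | power, early read of stage 1 only | power, fixed cut-off for both counts |
|---|---|---|---|
| 1 | 0.075 | 0.812 | 0.812 |
| 0.9 | 0.101 | 0.795 | 0.745 |
| 0.75 | 0.154 | 0.755 | 0.616 |
| 0.5 | 0.301 | 0.635 | 0.339 |

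For the same f, the fixed cut-off has the same false stop and lower power. Restoring 80% power for 0.05 against 0.1875 (f = 0.75) would need 43 patients in the optimal two-stage design (16 + 27) or 35 in the minimax design (16 + 19), against 17 now.

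An early read does not inflate the type I error. With f = 0.5 and a complete final count it is 0.032.

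**5. The expected-size formula.** As printed it gives 9 × 0.630 + 8 = 13.7. The correct form, n1 + (1 − P(stop)) × n2, gives the stated 12. The slip is in the explanatory text and not in the design.

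**The case for a change.** The best case for a change is that a primary decision rule should be executable from the text alone. The protocol fixes a week for one stratum and not for the other, and the stated 0.075 and 0.81 hold only if the read is mature. These tumours grow slowly, so a stage 1 with stable patients and no responses is plausible. That is when the wait is longest and the temptation to call the result early is greatest. A full-window pause also sits uneasily with the accrual forecast.

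Part of this stands. The read time is unwritten, and calling zero of nine prematurely would raise the false-stop risk. A clarifying sentence would do no harm.

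The rest does not stand. Continued enrolment during the wait is excluded by the conditional wording of section 13.2, which the Simon subsection repeats. The accrual statement is an expectation and not a commitment, and the even-accrual calculation used to show a conflict already presumes no pause. A zero count can also settle sooner than month 37, because progression ends treatment under section 5.6. The losses from an early read depend on assumed shares. They vanish if 0.25 is understood as the response rate at the time of the read. The worry that 0 of 9 in one stratum closes the other is strained, because each rule stands in its own stratum's paragraph with its own nine subjects.

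**Conclusion.** The plan can stand. The omission is a gap that an analyst fills in the ordinary way: a response maintained for 8 weeks counts whenever it occurs on treatment, stage 2 opens at the first such response, and zero of nine is declared when all nine have completed treatment, progressed or left it. On that reading 0.63, 0.05, 12, 0.075 and 0.81 are correct for each stratum.

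The residual cost is delay. With no responses and no early departures, the stop may not be settled until about month 37, on the assumption of even accrual of 17 patients over 24 months, but no patient beyond the ninth is enrolled meanwhile. The size of any harm from a premature read cannot be estimated from the documents. A fixed cut-off scan is a legitimate alternative design, but it would need its own justification of 25% by that scan, and with 17 patients it falls to power 0.62 or 0.34 if only 75% or 50% of responders are confirmed by then (assumed shares). The expected-size formula is a clerical slip with no effect on the design.
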